 Laptop Computer Desktop Computer Other
4. What methods and procedures will be used to safeguard the confidentiality and security of the identifiable study data and the storage media indicated above during and after the subject's participation in the study?

Participants will be assigned a study number in the Oncore database and the link will be maintained by the coordinator. Paper charts will be kept in a locked file cabinet in the coordinators locked office.

All portable devices must contain encryption software, per University Policy 5100. If there is a technical reason a device cannot be encrypted please submit an exception request to the Information Security, Policy and Compliance Office by clicking on url <http://its.yale.edu/egrc> or email [contact]

5. What will be done with the data when the research is completed? Are there plans to destroy the identifiable data? If yes, describe how, by whom and when identifiers will be destroyed. If no, describe how the data and/or identifiers will be secured.

Once the data analysis is complete and all publications have been finalized, the paper charts will be destroyed leaving only coded data.

6. If appropriate, has a Certificate of Confidentiality been obtained? N/A

SECTION V: POTENTIAL

Potential Benefits: Identify any benefits that may be reasonably expected to result from the research, either to the subject(s) or to society at large. (Payment of subjects is not considered a benefit in this context of the risk benefit assessment.)

Potential benefits associated with participation include early extubation and participants may spend less time in a critical care setting. The risk of pneumonia may also be reduced. The study does have placebo, so participants may not experience any benefit.

SECTION VI: RESEARCH ALTERNATIVES AND ECONOMIC CONSIDERATIONS

1. **Alternatives:** What other alternatives are available to the study subjects outside of the research?
The alternative is to not participate and be extubated per the standard of care

2. **Payments for Participation (Economic Considerations):** Describe any payments that will be made to subjects, the amount and schedule of payments, and the conditions for receiving this compensation.
There is no payment for participation

3. **Costs for Participation (Economic Considerations):** Clearly describe the subject's costs associated with participation in the research, and the interventions or procedures of the study that will be provided at no cost to subjects.
There is no cost to participate and study drug will be provided by Merck

4. **In Case of Injury:** This section is required for any research involving more than minimal risk, and for minimal risk research that presents the potential for physical harm (e.g., research involving blood draws).

- a. Will medical treatment be available if research-related injury occurs? Yes
- b. Where and from whom may treatment be obtained? If the patient is still hospitalized, care will be provided by the patient's treating physician or CTICU intensivist. If the patient has been discharged, while injuries or adverse events are not expected, care should be sought and the PI should be notified as soon as possible.
- c. Are there any limits to the treatment being provided? No

- d. Who will pay for this treatment? Yale School of Medicine and Yale-New Haven Hospital will not provide funds for the treatment of research-related injury. If there are study related injuries treatment will be provided. The patient or their insurance carrier will be expected to pay the costs of this treatment.
- e. How will the medical treatment be accessed by subjects? Care will be provided if necessary while the patient is hospitalized. If not in the hospital the patient should seek care as needed and notify the study team.

IMPORTANT

Will this study have a billable service? Yes No

A billable service is defined as any service rendered to a study subject that, if he/she was not on a study, would normally generate a bill from either Yale-New Haven Hospital or Yale Medical Group to the patient or the patient's insurer. The service may or may not be performed by the research staff on your study, but may be provided by professionals within either Yale-New Haven Hospital or Yale Medical Group (examples include x-rays, MRIs, CT scans, specimens sent to central labs, or specimens sent to pathology). Notes: 1. There is no distinction made whether the service is paid for by the subject or their insurance (Standard of Care) or by the study's funding mechanism (Research Sponsored). 2. This generally includes new services or orders placed in EPIC for research subjects.

If answered, "yes", this study will need to be set up in OnCore, Yale's clinical research management system, for Epic to appropriately route research related charges. Please contact [contact]

Are there any procedures involved in this protocol that will be performed at YNHH or one of its affiliated entities?

Yes No

If Yes, please answer questions a through c and note instructions below.

- a. Does your YNHH privilege delineation currently include the **specific procedure** that you will perform? Yes No
- b. Will you be using any new equipment or equipment that you have not used in the past for this procedure? Yes No
- c. Will a novel approach using existing equipment be applied? Yes No

If you answered "no" to question 4a, or "yes" to question 4b or c, please contact the YNHH Department of Physician Services ([name]) for prior approval before commencing with your research protocol.

IMPORTANT REMINDER ABOUT RESEARCH AT YNHH

Please note that if this protocol includes Yale-New Haven Hospital patients, including patients at the HRU, the Principal Investigator and any co-investigators who are physicians or mid-level practitioners (includes PAs, APRNs, psychologists and speech pathologists) who may have direct patient contact with patients on YNHH premises must have medical staff appointment and appropriate clinical privileges at YNHH. If you are uncertain whether the study personnel meet the criteria, please telephone the Physician Services Department at [contact]. **By submitting this protocol as a PI, you attest that you and any co-investigator who may have patient contact has a medical staff appointment and appropriate clinical privileges at YNHH.**

Additional Reference: Bleeding risk

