NCT03196167

Sugammadex and Decreased Time to Extubation

Study Protocol

6/19/2020

HRP-503B – BIOMEDICAL RESEARCH PROTOCOL
(2016-1)

Protocol Title: Efficacy and Safety of Sugammadex (2mg/kg) to shorten time-to-extubation among postoperative ICU patients following Aortic Valve Replacement, CABG surgery, or Aortic Valve Replacement with CABG surgery- a prospective randomized placebo- controlled trial.

Principal Investigator: [name].

Protocol Version Number and/ or Date: Version5, June 1, 2020

(If applicable) Clinicaltrials.gov Registration #: NCT03196167

INSTRUCTIONS

This template is intended to help investigators prepare a protocol that includes all the necessary information needed by the IRB to determine whether a study meets approval criteria. **Read the following instructions before proceeding:**

1. Use this protocol template for a PI initiated study that includes direct interactions with research subjects. Additional templates for other types of research protocols are available in the system Library.
2. If a section or question does not apply to your research study, type “Not Applicable” underneath.
3. Once completed, upload your protocol in the “Basic Information” screen in IRES IRB system.

SECTION I: RESEARCH PLAN

1. **Statement of Purpose:** State the scientific aim(s) of the study, or the hypotheses to be tested.
To demonstrate faster time to extubation after arrival in the cardiothoracic ICU in patients undergoing Aortic Valve Replacement (AVR), Coronary Artery Bypass Graft (CABG), or AVR/CABG combination surgery who receive study drug (Sugammadex 2mg/kg) as compared to placebo.
2. **Probable Duration of Project:** State the expected duration of the project, including all follow-up and data analysis activities.
Approximately 36 months
It is estimated that 3 subjects will be randomized per week allowing for data collection to be completed in 2 years for study start-up, with an additional 12 months for data analysis.
3. **Background:** Describe the background information that led to the plan for this project. Provide references to support the expectation of obtaining useful scientific data.

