2. Patients will be transferred to the CTICU intubated and on a propofol infusion and/or dexmedetomidine (Precedex) from the operating room. Both meds are used SOC.
3. Upon CTICU arrival, the patients surgeon and CTICU intensivist will determine if patient is able to proceed with fast-track extubation. Determination of continued eligibility based on the post-recruitment pre-randomization exclusion criteria will be determined by a member of the study team. Eligible patients will be randomized, investigational pharmacy will be contacted for study drug and within 30 minutes of the ICU admission, propofol will be discontinued. Precedex may be continued per clinical discretion.
4. The participant will be randomized to receive Sugammadex or placebo. The enrolled patients will be assigned to the study and control arms in a 1:1 ratio.
5. IDS will provide the Sugammadex (2mg/kg) vs. Placebo in a syringe. A qualitative train-of-four measurement will be obtained. The administration of the study drug and placebo compounds will be performed by CTICU nurses who will receive the drugs in a blinded fashion from the departmental research pharmacy. The study drug will be supplied by Merck.
6. The clinical care provider has the discretion to determine the appropriate ventilation settings on a case-by-case basis, in accordance with the suggestion that patients will be initiated on SIMV rate of 14 with 60% FiO₂, tidal volumes 8-10 ml/kg and PEEP of 7.
7. Ten minutes after the drug administration, if the patient can lift their head and remains hemodynamically stable, the patient will be switched to CPAP mode of ventilation for 30 minutes. At the end of the CPAP trial tidal volumes, Rapid Shallow Breathing Index (RSBI) and ABG will be assessed. The patient will be extubated if he/she is not hypoxic/ hypercarbic, has RSBI<100 and has TV >300 cc.
8. If a patient fails the 30-minute CPAP criteria, the ICU intensivist will be immediately notified. Every attempt will be made to correct the underlying cause of CPAP failure, and a prompt reassessment will be made as deemed appropriate by the intensivist to reattempt CPAP versus continuing controlled mechanical ventilation.

Study participation will end when the patient is successfully extubated. AE assessment will be performed in the period immediately following extubation.

5. Genetic Testing N/A

6. **Subject Population:** Provide a detailed description of the types of human subjects who will be recruited into this study.

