4. Determination that the patient will require prolonged mechanical ventilation possibly requiring muscle relaxation based on the intraoperative course and clinical judgment of the study PI or collaborating intensivists.
5. Intraoperative hypoxia or on arrival to the ICU. (Please see Study Flowchart).
6. Cardiac arrest
7. Sudden arrhythmia (Ventricular tachycardia runs/sudden bradycardia with improper pacemaker detection/function) precluding fast-track extubation protocol.
8. Need for two or more inotrope initiation precluding fast-track protocol. Only a single vasopressor/inotrope may be initiated without excluding the subject.
9. Postoperative ST changes.

10. A positive standard of care pregnancy test during your pre-operative evaluation

9. How will **eligibility** be determined, and by whom?

Eligibility at pre-op and post-op will be based on protocol specific inclusion and exclusion criteria and will be determined by the PI or Sub-I's in collaboration with the ICU attending physician

10. **Risks:** Describe the reasonably foreseeable risks, including risks to subject privacy, discomforts, or inconveniences associated with subjects participating in the research.

Sugammadex is generally safe and well tolerated. Potential risks associated with sugammadex are: hypersensitivity, including anaphylaxis/anaphylactic shock – previous trials suggest this risk is small. Cardiac arrhythmias including bradycardia & tachycardia where intervention is rare and responsive to usual treatment. Other reported risks include nausea, vomiting, constipation.

Bleeding was originally thought to be a side effect, but studies have since showed that Sugammadex falsely elevates the PTT without increasing bleeding risk. (see reference on last page.)

11. **Minimizing Risks:** Describe the way the above-mentioned risks will be minimized.

Patients will all be in a critical care environment and monitored very closely including: blood pressure, heart rate, and chest tube output will be tracked from arrival to the CTICU until extubation per ICU protocol. Subtle changes in the patient's hemodynamic status are easily seen and treated if necessary.

12. **Data and Safety Monitoring Plan:** Include an appropriate Data and Safety Monitoring Plan (DSMP) based on the investigator's risk assessment stated below. (Note: the HIC will make the final determination of the risk to subjects.)

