- e.) Unrelated: Adverse event is clearly not related to investigational procedures(s)/agent(s).

4. Plan for Grading Adverse Events:

The following scale will be used in grading the severity of adverse events noted during the study:

1. Mild adverse event
2. Moderate adverse event
3. Severe

5. Plan for Determining Seriousness of Adverse Events:

Serious Adverse Events:

In addition to grading the adverse event, the PI will determine whether the adverse event meets the criteria for a Serious Adverse Event (SAE). An adverse event is considered serious if it results in any of the following outcomes:

1. Death;
2. A life-threatening experience in-patient hospitalization or prolongation of existing hospitalization;
3. A persistent or significant disability or incapacity;
4. A congenital anomaly or birth defect; OR

5. Any other adverse event that, based upon appropriate medical judgment, may jeopardize the subject's health and may require medical or surgical intervention to prevent one of the other outcomes listed in this definition.

An adverse event may be graded as severe but still not meet the criteria for a Serious Adverse Event. Similarly, an adverse event may be graded as moderate but still meet the criteria for an SAE. It is important for the PI to consider the grade of the event as well as its "seriousness" when determining whether reporting to the IRB is necessary.

Only the following adverse events will be tracked. These AE's will trigger an immediate DSMB review; any incidence of anaphylaxis; unexplained hypotension requiring initiation of pressors; cardiac pacing within 5 minutes of drug administration; tachycardia, bradycardia or onset of atrial fibrillation; or increases in chest tube output considered clinically significant by the critical care team. The DSMB will be notified within 2 business days of determination by telephone or email. A written report will be provided within 7 days of the determination. Any incidents meeting SAE criteria will be reported per the IRB reporting policy.

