the time to extubation between the two groups. If necessary, covariate adjustment will be made using the multiple linear regression analysis method. Differences between means and 95% confidence intervals will be estimated to describe the magnitude of intervention difference between the two groups. As part of sensitivity analyses, the time-to-extubation outcome will be also analyzed by the Cox regression model. To compare the categorical adverse events between two groups, chi-square test or Fisher's exact test will be used.

Missing Data: Prevention is the most obvious and effective manner to control bias and loss of power from missing data. Therefore, several strategies (e.g., timely data entry and daily missing data report) will be imposed to limit the likelihood that missing data will occur during this study. This protocol will follow the intention to treat principle, requiring follow-up of all subjects randomized regardless of the actual treatment received.

Power analysis: Our 'in-house' historical data ($n = 73$) showed that after excluding outliers greater than the 80th percentile, patients undergoing isolated CABG demonstrated a mean of 8.39 hours to extubation (SD 2.89). Although we anticipate a Hawthorne effect demonstrating reduced time to extubation in both the active and placebo arms of the present study, we have conservatively chosen to maintain power based on historical data. We therefore estimate that 45 subjects per group will give us 90% power to detect a clinically relevant effect size of 2-hours difference between active and placebo groups at an alpha value of 0.05 using a two-sided two-sample t-test. To allow for post consent, pre-randomization study drop out, we will aim to enroll a total of 110 ($90 + 20 = 110$) subjects.

SECTION II: RESEARCH INVOLVING DRUGS, BIOLOGICS, RADIOTRACERS, PLACEBOS AND DEVICES

If this section (or one of its parts, A or B) is not applicable, check off N/A and delete the rest of the section.

A. RADIOTRACERS

 N/A

If NO, an FDA issued IND is required for the investigational use unless RDRC assumes oversight.

1. Check one: IND# *Write here* or RDRC oversight (RDRC approval will be required prior to use)

B. DRUGS/BIOLOGICS

 N/A

1. If an **exemption from IND filing requirements** is sought for a clinical investigation of a drug product that is lawfully marketed in the United States, review the following categories and complete the category that applies (*and delete the inapplicable categories*):

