9. Consent Waiver: In certain circumstances, the HIC may grant a waiver of signed consent, or a full waiver of consent, depending on the study. If you will request either a waiver of consent, or a waiver of signed consent for this study, complete the appropriate section below.

Not Requesting any consent waivers

Requesting a waiver of signed consent:

- Recruitment/Screening only (if for recruitment, the questions in the box below will apply to recruitment activities only)
- Entire Study (Note that an information sheet may be required.)

For a waiver of signed consent, address the following:

- Would the signed consent form be the only record linking the subject and the research? YES NO
- Does a breach of confidentiality constitute the principal risk to subjects? YES NO
- OR
- Does the research pose greater than minimal risk? YES NO
- Does the research include any activities that would require signed consent in a non-research context? YES NO

Requesting a waiver of consent:

Recruitment/Screening only (if for recruitment, the questions in the box below will apply to recruitment activities only)

Entire Study

For a full waiver of consent, please address all of the following:

- Does the research pose greater than minimal risk to subjects?
 - Yes If you answered yes, stop. A waiver cannot be granted.**
 - No**
- Will the waiver adversely affect subjects' rights and welfare? **YES** **NO**
- Why would the research be impracticable to conduct without the waiver? *Write here*
- Where appropriate, how will pertinent information be returned to, or shared with subjects at a later date? *Write here*

SECTION IV: PROTECTION OF RESEARCH SUBJECTS

Confidentiality & Security of Data:

1. What protected health information (medical information along with the HIPAA identifiers) about subjects will be collected and used for the research? Name, MRN, DOB, historical & current; medical history and laboratory results, and study related assessments.
2. How will the research data be collected, recorded and stored?

Data will be collected from the patient's medical record and kept in a paper file maintained by the study coordinator as source. Data will then be entered on a laptop computer in an OnCore database that is password protected and encrypted. Patient's will be assigned a study number in the research data base and the link will be maintained by the coordinator.

3. How will the digital data be stored? CD DVD Flash Drive Portable Hard Drive Secured Server

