If a patient fails the 30 minute CPAP criteria, the ICU intensivist will be immediately notified. Every attempt will be made to correct the underlying cause of CPAP failure, and a prompt reassessment will be made as deemed appropriate by the intensivist to reattempt CPAP versus continuing controlled mechanical ventilation.

It is estimated conservatively that the study personnel will randomize 3 patients per week allowing for data collection to be completed within 1 year of study commencement. Data analysis and dissemination of findings will be conducted over the subsequent 6 months by the study institution investigators per the publication plan below.

Blinded analyses of the data will be performed by the study investigators along with the departmental statistician in the Department of Anesthesiology at the Yale School of Medicine.

**Variables/Time Points of Interest:** The primary outcome is the time to extubation, which will be the duration from arrival to the ICU to the extubation time. Participants' blood pressure, heart rate, and chest tube output will be tracked from arrival to the CTICU until extubation per ICU protocol.

**Statistical Methods:** Baseline comparability. We expect that the randomization process will produce reasonably comparable groups. However, the adequacy of the randomization will be assessed by comparing the distribution of baseline demographic and clinical characteristics among the intervention groups. Comparability for continuous variables will be examined graphically and by summary statistics (means, medians, quartiles, etc.). Categorical variables will be examined by calculating frequency distributions.

**Proposed statistical test/analysis:** Positively skewed variables will be log-transformed prior to hypothesis testing. For the primary outcome, a two-sided Student's t-test will be used to compare the time to extubation between the two groups. If necessary, covariate adjustment will be made using the multiple linear regression analysis method. Differences between means and 95% confidence intervals will be estimated to describe the magnitude of intervention difference between the two groups. As part of sensitivity analyses, the time-to-extubation outcome will be also analyzed by the Cox regression model. To compare the categorical adverse events between two groups, chi-square test or Fisher's exact test will be used.

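### Unless an unavailable document sets a common window, adverse events are counted up to and just after each patient's own extubation, so a working drug shortens the active arm's observation time

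*Protocol*

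**What the plan says.** - **End of observation.** Protocol Section I item 4 (Research Plan): "Study participation will end when the patient is successfully extubated. AE assessment will be performed in the period immediately following extubation". No length is given for that last period.
- **Tracked measurements.** Protocol item 11 (Minimizing Risks): "blood pressure, heart rate, and chest tube output will be tracked from arrival to the CTICU until extubation per ICU protocol". The SAP repeats this under Variables/Time Points of Interest: "chest tube output will be tracked from arrival to the CTICU until extubation per ICU protocol".
- **Aim and effect size.** Protocol item 1: "To demonstrate faster time to extubation after arrival in the cardiothoracic ICU". The power analysis in item 13 claims "90% power to detect a clinically relevant effect size of 2-hours difference between active and placebo groups".
- **Tracked events.** Protocol item 12 gives a closed list. It includes "tachycardia, bradycardia or onset of atrial fibrillation; or increases in chest tube output considered clinically significant by the critical care team" with no time window. Cardiac pacing has a 5-minute post-dose limit.
- **Test.** Protocol item 13, repeated in the SAP: "To compare the categorical adverse events between two groups, chi-square test or Fisher's exact test will be used". The Cox model is reserved for time to extubation.
- **Named safety comparisons.** The SAP section on safety events for the manuscript names hypotension, anaphylaxis and bleeding (chest tube output). It does not name arrhythmia.

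**The concern.** The interval over which vital signs and chest tube output are tracked is the same interval as the primary outcome, and the trial aims to shorten it in one arm. The post-extubation assessment also starts at that event, so it moves with it. If sugammadex brings extubation forward, an event that accrues over time has less time to be seen on active. A crude comparison of proportions then favours the drug even when the drug has no effect on the event, and it could hide a modest true excess.

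The protocol names bradycardia and tachycardia among the potential risks of sugammadex (item 10), says use after cardiac surgery is limited by lack of supportive data (item 3), and claims safety as well as efficacy in its title. What is at stake is the interpretation of the between-arm safety table.

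**Working it through.** **Inputs from the documents (Protocol item 13):** placebo planning mean 8.39 h, SD 2.89 h, detectable difference 2 h, 45 per arm. **Assumed:** placebo event risk 20%; hazard shape; a post-extubation period of d hours, equal in both arms; dosing 0.5 to 1 h after ICU arrival where it matters.

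**1. The plan's own figure.** A two-sided two-sample t-test with difference 2, SD 2.89, alpha 0.05 and 90% power needs 44.86, so 45 per group; power at 45 is 0.901. The sample size reproduces.

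**2. Window ratio.** If the 2 h difference occurs, the active mean is 8.39 − 2 = 6.39 h. The ratio of windows is (6.39 + d)/(8.39 + d).

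**3. Spurious risk ratio, constant hazard, no true difference.** RR = [1 − 0.8^ratio]/0.20. The hazard ratio that would show as RR 1.0 is 1/ratio.

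| d (h) | Window ratio | Spurious RR | Masked hazard ratio |
|---|---|---|---|
| 1 | 0.787 | 0.81 | 1.27 |
| 2 | 0.808 | 0.82 | 1.24 |
| 4 | 0.839 | 0.85 | 1.19 |
| 8 | 0.878 | 0.89 | 1.14 |
| 12 | 0.902 | 0.91 | 1.11 |
| 24 | 0.938 | 0.94 | 1.07 |
| 0 (bound) | 0.762 | 0.78 | 1.31 |

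For placebo risks of 5% to 40%, RR is 0.84 to 0.87 at d = 4 and 0.94 to 0.95 at d = 24. With a 1 h effect, RR is 0.93 at d = 4 and 0.97 at d = 24. With no effect on extubation, it is 1.0.

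**4. Front-loaded risk.** Suppose risk halves every 2 h from dosing at s hours after arrival. The share of total risk captured is 1 − 0.5^((T − s + d)/2), with T = 6.39 or 8.39.
- d = 1, s = 1: 0.891/0.945 = 0.94.
- d = 4, s = 0.5: 0.968/0.984 = 0.98.

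These are ratios of captured risk; at a 20% placebo risk the RR is slightly nearer 1.

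**5. Against sampling error.** Even at the bound d = 0, the expected counts are 0.156 × 45 ≈ 7 and 0.20 × 45 = 9. Fisher on 7/45 versus 9/45 gives p = 0.78, and the RR of 0.78 has a 95% CI of 0.32 to 1.91. Exact Fisher rejection is 4.7% at 15.6% versus 20%, and 2.6% with 20% in both arms.

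**6. Which events are exposed.**
- *Tachycardia, bradycardia, atrial fibrillation:* exposed; no window is stated.
- *Hypotension:* exposed only if the 5-minute limit does not apply to it. Protocol item 12 separates hypotension from the pacing item with a semicolon; SAP Adverse Experience Reporting joins the two with "or".
- *Bleeding:* exposed if analysed as a cumulative volume or an ever/never event, much less so if analysed hourly. The metric is not defined.
- *Pacing within 5 minutes and early anaphylaxis:* not exposed.

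**7. Events per hour as an alternative.** With the step 4 risk shape, s = 0.5, d = 0 and no true difference, the rate ratio is (0.870/5.89)/(0.935/7.89) = 1.25, against the drug.

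**The case against.** **Three documents were not available:** the study flowchart, the DSMB charter and the SAP text before its Study Protocol heading. Any of them could set a window. This stands, and the point is conditional on it.

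**Observation does not stop dead at extubation.** The Research Plan provides for assessment afterwards, and the SAP has vital signs monitored continuously during and after drug administration. This also stands, so 0.78 is a bound and not the expected figure. But neither passage sets a common analysis window, and a period that starts at extubation dilutes the imbalance without removing it.

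**The SAP's named comparisons omit arrhythmia.** True. A reader might infer that the SAP's manuscript list commits to a biased arrhythmia comparison; it does not. Arrhythmia reaches a test only by joining the general adverse-event sentence to the protocol's tracked list. Of the three items the SAP does name, none is shown to be biased without a further reading of the text. The protocol's one numeric bleeding criterion, a pre-randomization exclusion, is hourly, which would favour the less sensitive metric.

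**Noise dominates.** Agreed at 45 per arm. A confidence interval conveys imprecision, however; it does not reveal a shift in one direction.

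**The stated aim is extubation time, with no safety hypothesis or margin.** Also true, and it limits the severity.

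**Conclusion.** The point holds as a minor one, provided no unavailable document sets a common window. The plan ties safety observation to an event that the drug is meant to move, then compares crude proportions. For arrhythmias that accrue over time, this favours active by roughly 6% to 19% on the risk-ratio scale at constant hazard (1 to 24 h after extubation), or about 2% to 6% if risk is front-loaded (1 to 4 h). Those sizes rest on an assumed 20% placebo risk and on the 2 h difference, which is what the trial is powered to detect and not a forecast.

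Two stronger readings are not supported. One is that the safety comparison would be likely to produce a false significant result: even at the bound, rejection is 4.7%. The other is that the trial's main conclusion is at risk: the primary outcome, the sample size and the event-triggered DSMB review do not depend on the comparison window.

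**What to change.** For the between-arm safety comparison, abstract the tracked adverse events, vital signs and chest tube output over one fixed window counted from study drug administration. It should be the same in both arms and independent of extubation, with its length chosen by the sponsor. Define the chest tube metric and report it at fixed times after dosing or per hour. Run the planned chi-square or Fisher tests on that window. Amend the data-collection wording in Protocol item 4 and in the SAP's Variables/Time Points of Interest; the clinical monitoring in Protocol item 11 need not change. If an unavailable document already sets such a window, citing it in the SAP is enough.

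Events per hour at risk should be at most a secondary summary, because it can bias against the drug when risk is front-loaded (step 7).

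Separately, reconcile Protocol item 12 and SAP Adverse Experience Reporting on which events the 5-minute limit covers.

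**Cost.** A short amendment and a little more chart abstraction. Source data already come from the "medical record and kept in a paper file maintained by the study coordinator as source" (Protocol Section IV). The consent and authorization wording must be checked to see that it covers data past the present end of participation. A fixed window also admits more background postoperative events. At any given clock time more active patients will already be extubated, so the comparison is of the whole strategy. It does not give the safety comparison adequate power.
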